#### *Life Skills Profile (LSP)*

Personal hygiene will be measured by scores on the Life Skills Profile (LSP; Rosen, Hadzi-Pavlovic, & Parker, 1989). The LSP consists of 39 clinician-rated questions on a four-point scale and measures various aspects related to daily life activities: self-care; non-turbulence; social contact; communication; responsibility. For this project, only the self-care ratings from the full LSP-39 will be completed by service providers. Current inpatient research on the use of CAT also uses this scale as a primary measure of the effectiveness of CAT. Scores will be obtained from the nursing staff not directly involved in the delivery of the finCAT intervention.

#### *Goal Attainment Scaling (GAS)*

Goal Attainment Scaling (GAS) will be employed as a sensitive measure of progress on individually defined goals. GAS has demonstrated good reliability and validity with severe mental illness populations (Hurn et al., 2006). Goal attainment scaling involves the setting of 3-5 goals, each operationalized on a 3-point scale. Goals are individualized to the client and assessment of progress is determined through consensus of the clinician and case manager.

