### ***Modified Cognitive Adaptation Training***

Locally, a CAMH study of a modified version of CAT in which an intensive 4-month period of CAT (applied by a CAT Clinician) with 5 months of maintenance (applied by the existing case manager) was recently tested for an outpatient schizophrenia population. This study found a comparable degree of gains in functional domains relative to Velligan's RCTs and those gains were sustained during the case manager led maintenance period (Kidd et al., 2014). This model was also recently tested for an early psychosis population at CAMH with CAT, once again, delivering similar improvements in functional outcomes (Kidd et al., 2019).

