**And**

## **(2) What are the attitudes of inpatient forensic occupational therapists and clinical teams towards implementing finCAT on their units?**

### **Methods**

#### ***Study Design Overview***

This study will expand on our preliminary work at CAMH. The study will be implemented on four CAMH general security forensic inpatient units. There will be four weeks of CAT Clinician--delivered treatment focusing on two goal areas – room organization and personal hygiene, followed by two months of maintenance by CAT Unit Champions with pre, post, and two-month follow-up, as well as project-end evaluations. In the first four weeks, we will conduct a trial of finCAT for two of the four inpatient general forensic units, followed by two months of finCAT maintenance with Unit CAT Champions supported by the CAT Clinician. This process would then be repeated on the remaining two general units at CAMH. Previous implementation of CAT has demonstrated gains within one-month; however, follow-up assessments were not conducted to determine if gains were maintained over time. While brief, this time period (i) reflects the intent of this study as a pilot test of feasibility and, (ii) aligns with this circumscribed version of CAT (as compared to the more comprehensive community version with broader outcome domains). Data will be collected from both primary participants (inpatients) and the clinical team.

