**Data Analysis**

For this analysis, primary variables are CIRS, GAS, and LPS scores. Secondary variables are the EBPAS and additional qualitative measures of care provider attitudes.

The data analysis is as follows: (1) A descriptive profile of demographic and baseline data will be developed; (2) We will develop a descriptive profile of session attendance; (3) We will compare pre/post/follow-up measures within treatment groups using ANOVA with posthoc analyses to determine change between time points. Cohen’s d will be used to assess effect size. For all analyses  $p < .05$  will be used as the level of significance.

Transcripts from focus groups and individual interviews will be thematically analyzed using a content analysis strategy as articulated by Hsieh & Shannon, 2005. The analysis will be validated through the use of 2 independent coders and full team reviews of code summaries.

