**Appendix II – CAT Referral Form**

Cognitive Adaptation Training Referral			
Unit/Service at time of Documentation			
Referral Requested By			
Primary Nurse or Case Manager			
Date of Referral			
Who should be contacted for information or questions regarding this referral?			
Name			
Extension			
Current Psychiatric Status			
 At baseline	 Persistent negative symptoms	 Active substance use	
 Actively psychotic	 Persistent positive symptoms		
 Has insight into symptoms	 No persistent symptoms		
Housing Type			
 Inpatient	 With Family/Spouse	 Boarding Home	
 Independent	 Homeless/Shelter	 Meals Provided	
 Supported	 Transitional	 Housing at Risk	
Approx. Length of Time in Current Housing			
Approx. Time to Discharge or Transfer		 1-2 months	 3-6 months
		 6 months +	
– NOTE TO OUTPATIENT CLINICIANS – PLEASE COMPLETE PRE-VISIT HOME SAFETY RISK ASSESSMENT POWERFORM			
Client Factors			
 Paranoia	 Engaged with Staff	 Independent in ADLS	 Involved in Work
 Insight into Illness	 Engaged with Family	 Hoarding	 Involved in School
 Antisocial PD	 Social Involvement	 Infestations/Bedbugs	 Involved in Volunteering
Clinical Goals			
 CAT Clean Rooms	 Personal Hygiene	 Social Skills	 Diet/Weight Management
 Home Safety	 Dental Hygiene	 Stress Management	 Employment Connection
 Attendance	 Housing Keeping	 Budgeting	 Education Connection

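### Does the missing scoring rule for Goal Attainment Scaling leave a primary result open to choice?

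*Combined protocol and SAP*

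**What the plan says.** The Goal Attainment Scaling (GAS) section gives two rules. First, "Goal attainment scaling involves the setting of 3-5 goals, each operationalized on a 3-point scale". Second, "Goals are individualized to the client and assessment of progress is determined through consensus of the clinician and case manager". It does not label the three levels, state the level at Pre-CAT, weight the goals or define a summary score.

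The Data Analysis section states: "For this analysis, primary variables are CIRS, GAS, and LPS scores" (LPS is evidently a slip for LSP). It compares pre, post and follow-up "measures within treatment groups using ANOVA with posthoc analyses to determine change between time points", at p < .05, and adds that Cohen's d "will be used to assess effect size" without naming the standard deviation. Table 3 schedules GAS at Pre-CAT, Post-CAT and Follow-Up.

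On roles, the outpatient study described under Modified Cognitive Adaptation Training had "5 months of maintenance (applied by the existing case manager". In the present study the intensive phase is "followed by two months of maintenance by CAT Unit Champions" (Study Design Overview). Besides these, a case manager appears only in the referral form's field "Primary Nurse or Case Manager" (Appendix II).

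**The concern.** A primary variable with a significance test normally has a score that two analysts would compute in the same way. Here four items are open: the starting level, the combining rule, the raters' study roles and the standardiser for d. If different permitted rules gave different verdicts, choosing one after seeing the data would push the false-positive rate above 5%. If the starting level were the lowest by construction, a significant rise would say little. A d that shifted with such choices could mislead later planning, and The Proposed Project names optimal powering as one use of the data.

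The contrast with the other two primary variables sharpens the impression. The Clutter Image Rating Scale has two blinded raters and a stated mean. The Life Skills Profile is scored by nurses not directly delivering the intervention. GAS, arguably the most subjective of the three, has neither safeguard in writing.

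**Working it through.** **Inputs.** From the documents: 24 participants (Participants), 3 to 5 goals on 3 levels (GAS section), three visits and alpha .05 (Data Analysis). Assumed: two-sided tests; equal shares of 3, 4 and 5 goals; Pre-CAT ratings spread 25/50/25% over the levels; Post and Follow-Up with the same mean; and three settings for correlation between a participant's goals (stronger, weaker, none).

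**1. The plan's own figure.** 4 units × 6 = 24. The plan gives no power figure. A paired t-test with n = 24, as a stand-in for the pre/post comparison, has 65%, 86% and 96% power at d = 0.5, 0.65 and 0.8 (SD of change), and 80% at about 0.60. That fits the plan's claim of medium-large effects.

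**2. Why the usual scores agree.** Let participant i have kᵢ goals and mean goal level Mᵢ.
- Sum score: Sᵢ = kᵢ × Mᵢ.
- T-score with the assumed inter-goal correlation of 0.3: Tᵢ = 50 + 10 × Sᵢ / √(0.7kᵢ + 0.3kᵢ²) = 50 + 10 × Mᵢ × √(kᵢ / (0.7 + 0.3kᵢ)).

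kᵢ does not change between visits, so constants cancel in the change and the three scores differ only in each participant's weight.

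| Goals | Mean | Sum | T-score multiplier |
|---|---|---|---|
| 3 | 1 | 3 | √(3/1.6) = 1.37 |
| 4 | 1 | 4 | √(4/1.9) = 1.45 |
| 5 | 1 | 5 | √(5/2.2) = 1.51 |

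The T-score is within about 10% of proportional to the mean (1.51/1.37 = 1.10). The sum weights 5 goals against 3 by 5/3 = 1.67.

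**3. Simulation of mean against sum** (repeated-measures F, three visits).
- No change: each rejects in about 5%, and at least one of the two in about 6%, at all three correlation settings.
- Average rise of 0.2 level, stronger correlation: mean about 46%, sum about 45%. They disagree in 5 to 7% of studies across the three settings.
- A second model (latent change, Pre at 50/35/15% from lowest to highest, pre/post t-test): mean 76.0%, sum 75.8%, T-score 76.3%.

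**4. Where larger figures come from.** Adding two share-of-goals scores (goals at the middle level or above, goals at the top level) raises the chance of at least one false rejection to 11 to 12%. At a rise of 0.2 level with the stronger correlation, not all four rules agree in 43% of studies. Entering goals as separate rows rejects in 21%, 12% or 5% as correlation falls to none. No section proposes share scores or goal-level rows.

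**5. Starting level** (second model, no average latent change, mean score). Significant improvement occurs in 100% of studies if every goal starts at the lowest level, about 3% if every goal starts at the middle, and about 20% with the mixed start. The lowest-level result follows from the scale: such scores can only stay or rise.

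**6. Size of d.** For an average rise of 0.3 level with freely rated Pre and the stronger correlation, d on the mean score is 0.58 (SD of change), 0.58 (pooled SD) or 0.57 (Pre SD). If instead every goal starts at the lowest level and 30% move up one, with correlation ρ between goals:

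Var = 0.3 × 0.7 × average over k = 3, 4, 5 of [1 + (k − 1)ρ]/k.

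- ρ = 0.5: 0.21 × 0.631 = 0.132, SD 0.364, d = 0.3/0.364 = 0.82.
- ρ = 0.28, matching the observed correlation of goal changes in the free-Pre case: 0.21 × 0.468 = 0.098, SD 0.313, d = 0.96.

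Like for like, the starting level moves d from 0.58 to about 0.96. On a pooled SD the fixed start at ρ = 0.5 gives 0.82 × √2 = 1.17, only because a Pre SD of zero is averaged in.

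**The case for a change.** The strongest case is that the gap is genuine and no other section closes it: the source cited for GAS is not even in the reference list. Feasibility status does not excuse it, because the plan still sets a primary test at .05 and says that its data will inform later powering. The starting level can by itself decide the verdict (100% against 3%), and about six sentences would settle everything without an added visit or rating.

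Part of this stands. The text is incomplete, and a starting level fixed at the bottom would make the pre/post test uninformative. But the documents do not describe that condition. Table 3 lists GAS at Pre-CAT in the same way as the two rated scales, which fits a rating at least as well as an assigned level. Nor would a sentence on scoring remove the milder form: with the mixed start, half the goals begin at the lowest level and 20% of no-change studies still show a rise. That follows from a bounded scale and a single group, and the plan declares the single group.

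The powering argument is weaker than it looks. Putting d of 0.58, 0.83 or 1.17 into a two-arm formula gives 48, 24 or 13 per arm at 80% power. Those are pre/post values from one group, not differences between arms, and the step from 0.58 to 1.17 changes starting level, goal correlation and standardiser together. No section says that d for GAS will set a later sample size.

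On raters, the plan does state a two-person consensus. The roles are ambiguous, probably carried over from the outpatient model. The text neither shows nor excludes that a rater delivers finCAT, so no bias is demonstrated.

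**Conclusion.** The concern identifies missing detail, not an error, and no change to the plan is required. An analyst given several goals per person, a 3-point scale and an instruction to compare scores by ANOVA would use one level score per participant. Mean, sum and T-score then lead to nearly the same conclusion: about 6% rather than 5% false rejections if one could pick between mean and sum, and disagreement in 5 to 7% of studies at a rise of 0.2 level. These sizes rest on the assumed rating distribution and goal correlations; the near-equivalence of the scores follows from the algebra.

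Two sensitivities remain for whoever reads the results. The size of d depends on the starting level (0.58 against about 0.96 in a matched comparison) and on the standard deviation used, so a reported GAS d needs its standard deviation beside it. The test would lose its meaning if all goals were placed at the lowest level by design, which the documents do not say. In a single-group feasibility study of 24 that declares itself underpowered, both are matters of sensible analysis and reporting.

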#### *Evidence-Based Practice Attitude Scale (EBPAS)*

The attitudes of the team members towards finCAT will be measured using the Evidence-Based Practice Attitude Scale (EBPAS; Aarons, 2004) adapted to specifically target attitudes towards CAT. The EPBAS is a self-report questionnaire consisting of 15 items measured on a 5-point Likert scale ranging from 0 ('Not at

all’) to 4 (‘To a very great extent’) and consists of four subscales: (1) appeal, (2) requirements, (3) openness and (4) divergence.

*Essen Climate Evaluation Schema (Essen CES)*

The therapeutic alliance on the unit will be measured by clinician and client ratings on the Essen Climate Evaluation Schema (Essen CES; Schalast et al., 2008). The Essen CES is a 15-item questionnaire measured on a 5-point Likert scale ranging from ‘Not at all’ to ‘Very Much’ and consists of three subscales: (1) Patient’s Cohesion, (2) Experienced Safety, and (3) Therapeutic Hold. For this study, client and clinician ratings on the Therapeutic Hold subscale will be collected.

[figure not shown]
*Qualitative Care Provider & Participant Attitudes*

The attitudes of the team members and participants towards finCAT will also be measured using a qualitative feedback form created for this study. Questions will target attitudes towards finCAT, perceptions of the impact of finCAT, and perceptions of team tension or conflict arising or abating during the implementation of finCAT. Small focus groups with healthcare providers and individual interviews with interested clients will be facilitated by student investigators. Interviews will be audio-recorded and transcribed verbatim.

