### ***The questions for this project are:***

#### **(1) Is finCAT feasible for forensic inpatient populations with a schizophrenia spectrum diagnosis?**

Based on preliminary work we hypothesize that finCAT will prove acceptable to patients and inpatient staff and will demonstrate positive outcomes with respect to functioning and inpatient room organization.

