#### ***Participants***

Participants will be enrolled from four CAMH forensic inpatient units (medium security excluded). A total of 6 participants will be recruited from each unit for a total of 24 participants. Attrition is expected to be minimal given the inpatient context and previous delivery of CAT with this population. While previous data are not available for formal power analysis, this sample size is anticipated to prove adequate for the detection of medium-large effects though must be considered underpowered and will inform future power analysis.

Specific criteria include:

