**Recruitment**

All participants will be recruited through CAMH Complex Care & Recovery inpatient forensic services. Following orientation to the study for clinical teams, clinical staff will (i) first clear involvement with the individual’s MRP and then (ii) approach potential participants who they consider appropriate using the script provided in Appendix I. Participants will then be screened by research personnel via a referral form (Appendix II) to identify any potential exclusion factors (high paranoia, primary issue of hoarding, etc.).

Potential participants who indicate further interest in hearing more about the study and provide assent to be contacted by a member of the research team will then be contacted by a member of the research team who will engage them in a written informed consent process. At that meeting, participants will be provided with a clear explanation of the objectives, procedures, rights as a research subject, risks and benefits of the study and all questions will be answered prior to obtaining their signature on the informed consent document. If a participant is incapable of providing written informed consent, a member of the research team will meet with them and their Substitute Decision Maker (SDM) and provide the same briefing as described above prior to obtaining the SDM's signature on the SDM informed consent form. If the participant has the capacity to understand the significant of the research, an assent form will also be completed with the participant. If they are not interested in participating (dissent/do not assent), these prospective participants will not be included in the study, but will be informed they will be eligible to receive CAT at a later date. A member of the research team will connect with the participant at 1-month into the study to confirm their continued assent to participate. Should the participant want to withdraw at this time they will be removed from the study and a member of the research team will ask the participant if the previously collected data may or may not be used in data analysis. Consent for audio recording during the focus group will be obtained at both consent timepoints (entry and 1-month). If a participant does not consent to have their responses audio recorded during the focus group they may choose to have an individual interview that is not recorded.

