All forensic inpatients identified by their treatment team as potential CAT recipients will be given the option to participate in the research study. Participation in the study is voluntary. The decision to participate will not affect patients' receipt of usual treatment or clinical services. Participants will be informed that they have the option of terminating their participation in the study and the intervention at any time, without consequence.

A delegated Research Coordinator will access personal health information (PHI) in I-CARE to determine eligibility of clients to participate in the research study. No PHI will be collected. PHI will not be accessed until informed consent or assent is obtained. .

For participating in the 30 individual interviews following participation in the finCAT intervention, clients will receive \$10 value in gift cards from Gifts of Light or Stamp Store stamps depending on preference. Care providers will not be reimbursed for their time as focus groups will occur during work hours.

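### Evidence on client acceptability may be too favourable: interviews are self-selected and late, clients who stop have no described way to give a view, and only transcripts have a stated analysis

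*Combined protocol and SAP*

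**What the plan says.** Patient acceptability is part of the first study question. Under The questions for this project: "we hypothesize that finCAT will prove acceptable to patients and inpatient staff". The Proposed Project section adds that the data should show what needs changing in finCAT.

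The Qualitative Care Provider & Participant Attitudes subsection of Measures names two client sources. One is a feedback form for staff and participants. The other is an interview: "Small focus groups with healthcare providers and individual interviews with interested clients will be facilitated by student investigators". Interviews are to be recorded and transcribed.

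On timing, the Attitudes row of Table 3 is marked at Follow-Up only. The Study Model shows one client interview, after the Follow-Up block.

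On people who leave, Recruitment says of the 1-month assent check: "Should the participant want to withdraw at this time they will be removed from the study". The Safety Protocol also lets involvement be ended early when finCAT is not helping or is not tolerated.

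On analysis: "Transcripts from focus groups and individual interviews will be thematically analyzed". The only attitude measures listed as secondary are those of care providers. Someone who does not agree to recording has another option: "they may choose to have an individual interview that is not recorded".

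**The concern.** Clients who disliked finCAT, stopped it or were taken off it can best show where it is not acceptable and why. Under the stated rules they are the least likely to be heard. They may not volunteer for an interview, and if they have left before Follow-Up nothing provides for their views to be collected. A client who is interviewed without recording, or who only fills in the form, gives material for which no analysis is described.

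The acceptability part of the hypothesis would then be judged mainly on self-selected completers. The study would also lose first-hand reasons for stopping, which it needs in order to adjust the intervention. Those reasons are hard to recover reliably later.

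**Working it through.** **Denominator.** Participants states: "A total of 6 participants will be recruited from each unit for a total of 24 participants". Check: 4 units × 6 = 24, which agrees. One client is 1/24 = 4.2% of the sample and three are 3/24 = 12.5%.

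**Sources of evidence on client acceptability**

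| Source | Who | When | Stated analysis |
|---|---|---|---|
| Feedback form | Participants and staff, no restriction | Follow-Up (Table 3, reading the Attitudes row as covering the form) | None |
| Recorded client interview | Interested clients | After Follow-Up (Study Model) | Content analysis of transcripts |
| Unrecorded interview | A person who declines recording; worded for the focus group | Not stated separately | None |
| Session attendance, drop-out | Clients | During the study | Descriptive profile of attendance; drop-out to inform later trials |
| Provider focus groups | Staff, asked how clients responded | After Follow-Up | Content analysis of transcripts |

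Only the second row gives clients' own views with a stated analysis, and it is limited to those who volunteer late in the study.

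**Timing against stopping.** Study Design Overview gives four weeks of clinician-led finCAT and then two months of maintenance before follow-up. The assent check is at 1 month. A person who withdraws at that check is asked whether data already collected may be used, but no attitude data exist by then.

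**How much could it matter?** The documents give no interview uptake and no acceptability threshold, and they plan no acceptability percentage. The figures below rest on assumed rates. They show sensitivity only and do not correspond to a planned estimate.

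*Bounds.* If k of 24 are interviewed and f are favourable, the favourable share among all 24 lies between f/24 and (f + 24 − k)/24. Taking about 90% of interviewees as favourable:

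- k = 20, f = 18: 18/24 = 75% to 22/24 = 92%
- k = 16, f = 14: 14/24 = 58% to 22/24 = 92%
- k = 12, f = 11: 11/24 = 46% to 23/24 = 96%

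*Selective uptake.* Let p be the true favourable share, 0.9 the uptake among favourable clients and q the uptake among the others. The share seen is 0.9p / (0.9p + (1 − p)q).

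| q | p = 0.60 | p = 0.70 |
|---|---|---|
| 0.3 | 0.54/0.66 = 82% | 0.63/0.72 = 88% |
| 0.5 | 0.54/0.74 = 73% | 0.63/0.78 = 81% |
| 0.7 | 0.54/0.82 = 66% | 0.63/0.84 = 75% |
| 0.9 | 0.54/0.90 = 60% | 0.63/0.90 = 70% |

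With equal uptake (last row) there is no distortion.

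**A side inconsistency.** Recruitment refers to a number of interviews: "For participating in the 30 individual interviews following participation in the finCAT intervention". That is 30 − 24 = 6 more than the clients enrolled. A dropped unit (30-minute interviews) is a likely explanation.

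**The case against.** Several points on the other side are sound.

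- **The feedback form.** A reader might infer that client views come only from interested clients. They do not, because the form covers participants without that restriction. It narrows the gap but does not close it: it falls at Follow-Up, so those who have left miss it, and it has no stated analysis.
- **The unrecorded interview.** A reader might infer that clients who refuse recording are lost. The protocol offers them an interview, and Data Analysis does not say that notes are excluded. What remains is that no analysis of notes is described, and that the option is worded for a focus group although clients are interviewed individually.
- **Voluntariness.** Describing interviewees as interested may mean only that taking part is voluntary. Some self-selection will remain under any ethical plan, and someone who has withdrawn may decline further contact. That is a reason to invite everyone and report who declined.
- **Attrition.** Participants says: "Attrition is expected to be minimal given the inpatient context and previous delivery of CAT with this population". If so, few will leave early. Self-selection for the interview still operates with no attrition at all.
- **Other evidence.** Attendance, drop-out and the provider focus groups will show some non-acceptance, and clients are asked what they did not enjoy. Attendance and drop-out show that people stopped but not why; staff accounts are second-hand; and the client question reaches only those interviewed. The Safety Protocol has researchers discuss reasons when they withdraw someone, but does not say that the participant's view is recorded as data.

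**Conclusion.** The concern holds as a risk. Following the plan, patient acceptability would be judged mainly in self-selected clients who reach Follow-Up, with no described route for those who stop and no stated analysis for forms or unrecorded interviews.

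A reader might go further and conclude that acceptability is overstated. The documents do not support that. It requires lower uptake among dissatisfied clients, for which they give no figure. The illustrative overstatement runs from 0 to 22 percentage points (60% seen as 60% to 82%) purely according to the assumed uptake, and the planned content analysis yields themes, not a percentage. Nor is the mention of 30 interviews evidence of bias; it is a separate wording correction.

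For a 24-person feasibility study this is an inexpensive improvement worth making before interviews begin. It does not invalidate the design.

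**What to change.** 1. **Measures, Qualitative Care Provider & Participant Attitudes:** invite every enrolled participant, voluntarily, to complete the existing feedback form and the interview. Offer anyone who stops finCAT or leaves the study the form, or a few of the client questions in Appendix III, when they stop. They may decline. This changes nothing about when or why participation ends.
2. **Table 3:** add an Attitudes assessment at early stopping.
3. **Data Analysis:** list client attitudes as a secondary variable, and analyse feedback forms and written notes of unrecorded interviews alongside transcripts.
4. **Reporting:** out of 24, give the numbers invited, interviewed, declined and stopped, beside attendance.
5. **Recruitment:** reconcile the focus-group recording wording with the individual client interviews, and state whether 30 is a number of interviews or a duration.

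The cost is protocol and consent wording, a few short extra contacts by the same student investigators, and a few more $10 vouchers (24 × $10 = $240 in total if every client were interviewed). The drawback is that notes and forms are thinner than transcripts, and some people who stop will still decline.
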